2.1.3 Partial information for dates

The heart failure diagnosis date, or the time from Chagas disease diagnosis date, will be considered as the first day of the reported month if only the month and year are provided. If only the year is reported, January 1st will be assumed. The same imputation logic will be applied to the start and end dates of adverse events or any other date when only partial information is available (month/year or just year).

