Clinical Development

PARACHUTE: Prevention And Reduction of Adverse outcomes in Chagasic Heart failUre Trial Evaluation.

Clinical Study Protocol CLCZ696B3302

**A multicenter, prospective, randomized, open-label,
blinded-endpoint, Phase 4 study to evaluate the efficacy
and safety of sacubitril/valsartan compared with enalapril
on morbidity, mortality, and NT-proBNP change in patients
with chronic Chagas' cardiomyopathy**

Statistical Analysis Plan (SAP)

Document type: SAP Documentation

Document status: Version 2.1

Release date: 29-Apr-2025

Number of pages: 42

Property of Novartis
For business use only
May not be used, divulged, published or otherwise disclosed
without the consent of Novartis

Document History – Changes compared to previous final version of SAP

Version	Date	Changes
1.0	05/11/2020	First Version
2.0	09/04/2025	
• Section 2.6.1 and 2.6.2.4 - Recurrent events included as secondary endpoint.• Section 2.6.1 and 2.6.2.3 - Definition of days alive and out of hospital modified to within one year from randomization.• Section 2.8 - NT-ProBNP evaluation at month 8 included as an exploratory endpoint.• Section 2.5.2.1 - Definition of cardiovascular death included.
		
• Section 2.5.3 - Supplementary analysis for the primary outcome added to account for missing NT-ProBNP values and recurrent events.• Section 2.5.3 - Supplementary analysis for the primary outcome added to account for total death.• Section 2.8 - Exploratory analysis of the time-dependent interaction of SGLT2 inhibitors with treatment included.• Section 2.9 - Subgroup analysis comparing randomizations of COVID-19 during the pandemic period (and after)• Sections 2.5.1.1 and 2.5.1.2 - Estimands definitions
2.1	29/04/2025	
• Section 2.2 - Per protocol set definition updated.• Section 2.1.3 - Added imputation logic for partial missing dates• Section 2.4.1 - Calculation of drug adherence• Section 2.5.2 – Clarification of time to event censoring.• Section 2.9 - Subgroup analyses variables updated

Table of contents

	Table of contents	3
	List of abbreviations	5
1	Introduction	6
1.1	Study design.....	6
1.2	Study objectives and endpoints	8
2	Statistical methods.....	9
2.1	Data analysis general information	9
2.1.1	General definitions	10
2.1.2	Randomization	12
2.1.3	Partial information for dates.....	12
2.2	Analysis sets	13

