2.6.3 Safety analyses

The safety and tolerability assessments are:

- a. Physical examination;
- b. Vital signs (sitting systolic and diastolic blood pressure, and pulse);
- c. Pregnancy assessment;
- d. Electrocardiogram;
- e. Adverse events;
- f. Serious adverse events;
- g. Adverse events of special interest:
 - Arrhythmia
 - Angioedema
 - Symptomatic hypotension
 - Hyperkalemia
 - Renal dysfunction

For all safety analyses, the SAF will be used. All listings and tables will be presented by treatment arm.

Safety summaries (tables, figures) include only data from the on-treatment period with the exception of baseline data which will also be summarized where appropriate (e.g., change from baseline summaries). In addition, a separate summary for death including on treatment and post treatment deaths will be provided. In

particular, summary tables for the Adverse Events (AEs) will summarize only on-treatment events, with a start date during the on-treatment period (treatment-emergent AEs).

The on-treatment period lasts from the date of first administration of study treatment to 30 days after the date of the last actual administration of any study treatment.

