2.6.3.3 Adverse events

All information obtained on AEs will be displayed by treatment arm and listed by subject.

The treatment emergent adverse events (events started on or after the first dose of study medication or events present prior to the first dose of study medication but increased in severity based on preferred term on or after the first dose of study

medication until 30 days after study's treatment last dose) will be summarized by primary System Organ Class (SOC) and Preferred Term (PT).

Separate summaries will be provided for study medication-related AEs, death, SAEs, other significant AEs leading to discontinuation.

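### SAP 2.1.3 imputes partial adverse event start dates with no floor at first dose, so some post-dose events fall out of the on-treatment AE and AESI summaries

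*SAP*

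**What the plan says.** SAP 2.1.3 opens with heart failure and Chagas diagnosis dates. A date known to month and year "will be considered as the first day of the reported month if only the month and year are provided". For less complete dates, "If only the year is reported, January 1st will be assumed". The section then widens the scope: "The same imputation logic will be applied to the start and end dates of adverse events or any other date" for which only part is available. The document history lists this under version 2.1 as "Added imputation logic for partial missing dates".

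The safety sections depend on start dates. SAP 2.6.3 says AE tables "will summarize only on-treatment events, with a start date during the on-treatment period". It defines that window as follows: "The on-treatment period lasts from the date of first administration of study treatment to 30 days after the date of the last actual administration". SAP 2.6.3.3 defines treatment-emergent events as "events started on or after the first dose of study medication", or as events already present that worsen on treatment. The same section lists all AE information by subject.

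Neither document bounds an imputed AE date by first dose. The only guard against reversed dates is in SAP 2.4.1, which sets negative dosing intervals to zero days. The protocol has no partial-date rule. Protocol 10.1.1 asks for AE details, including start and end dates, only as far as they can be obtained, so partial dates are foreseeable.

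**The concern.** The earliest possible day is a common convention for a diagnosis that precedes the study. It does not suit an AE start date, because the table counts the event only if that date is on or after first dose. When the known month or year contains the first dose, the earliest day of that period comes before dosing for nearly every participant.

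The loss is concentrated in the weeks just after first dose. That is the titration period, in which protocol 3.2.1 directs attention to symptomatic hypotension, renal function and potassium. Three of the five AESI categories in SAP 2.6.3.4 are of this kind, and AESI incidence is compared between arms by Fisher's exact test.

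**Working it through.** **1. A plan figure to reproduce.** The plan gives no figure for the date rule. The nearest figure its inputs can reproduce is the 302 expected events, whose planning rates are used in step 6. With exponential times, uniform 18-month accrual and a 36-month study, P = 1 − [exp(−1.5λ) − exp(−3λ)]/(1.5λ).
- Enalapril, λ = 0.20: P = 0.360; × 450 = 162.0.
- Sacubitril/valsartan, λ = 0.16: P = 0.3006; × 450 = 135.3.
- Total 297.3 against 302, which is 1.6% lower.

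**2. One participant.** Take first dose on 10 March 2021.
- An AE on 24 March recorded as March 2021 becomes 1 March, 9 days before first dose.
- An AE on 15 November recorded as 2021 becomes 1 January, 68 days before first dose.
- Neither is then treatment-emergent by start date.

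**3. Loss among partially dated AEs.** Let L be the period length (365.25/12 = 30.44 days for a month, 365.25 for a year). First dose is uniform over calendar days and onset is uniform over the w days from first dose. An AE is lost if it falls in the same period as first dose and first dose is not on day 1 of that period.
- If w ≤ L: loss = (L − 1)/L − (w − 1)/(2L).
- If w > L: loss = (L − 1)/(2w).

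| Onset window | Month-only | Year-only |
|---|---|---|
| 3 weeks (w = 21) | 29.44/30.44 − 20/60.88 = 64% | 364.25/365.25 − 20/730.5 = 97% |
| 6 weeks (w = 42) | 29.44/84 = 35% | 364.25/365.25 − 41/730.5 = 94% |
| 12 weeks (w = 84) | 29.44/168 = 17.5% | 364.25/365.25 − 83/730.5 = 88% |
| 1 year (w = 365) | 29.44/730 = 4% | 364.25/365.25 − 364/730.5 = 50% |

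A calendar-date simulation with 2,000,000 draws gives the same percentages. With a floor at first dose the loss is 0% in every cell.

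**4. The opposite error.** An AE starting 31 to 60 days after last dose is outside the window. It is pulled in if the first of its month is no more than 30 days after last dose. The first formula with w = 30 applies: 29.44/30.44 − 29/60.88 = 49% for month-only dates. The simulation agrees.

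**5. End dates.** With a complete start date and a month-only end date, an AE lasting 7 days ends before it starts with probability (30.44 − 1 − 7)/30.44 = 74%. The SAP's AE tables use start dates, and it specifies no AE duration analysis, so no specified table changes.

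**6. Endpoint dates, if any were partial.** At the planning rates, about 2% of month-only and 25 to 26% of year-only endpoint dates would fall before randomization. The pairwise effect was simulated on time to first CV event only, with 450 per arm, 60 trials per setting and an assumed 1 to 10% of event dates partial.
- Month-only dates change at most 0.07% of pairs; year-only dates 0.07 to 0.8%.
- With partial dates equally frequent in both arms, the win ratio moves by about 0.001 or less.
- With 10% year-only dates in the enalapril arm alone, it moves from about 1.22 to 1.25.

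**The case against.** The strongest reply is that this is a small wording matter. Missing values are queried (protocol 11.2). Potential AESIs are followed up with the site and have their own form (SAP 2.6.3.4), so they are among the events least likely to lack a full date. The by-subject listings keep every AE visible, and the worsening clause may retain some. All of this stands and limits the likely number of affected events. It does not make the rule right, because the safety summaries are built from the imputed date.

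A reader might go further and infer three things that the documents do not support.
- **That the rule biases the primary analysis.** Its wording does reach endpoint dates. But CV events are adjudicated (SAP 2.5.1), protocol 11.3 requires full source verification of primary-variable data, and nothing shows that any endpoint date will be partial. Step 6 finds almost no effect when partial dates are balanced.
- **That the error only removes events.** Step 4 shows that it also adds some.
- **That it favours one drug on safety.** The trial is open-label at sites, so equal date completeness cannot be taken for granted, but no difference between arms is shown.

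The rule is also not entirely free of effect on diagnosis dates. A year-only heart failure diagnosis in November, in a participant randomized the next February, moves from the subgroup of 1 year or less to the next one (SAP 2.9). That is a limited cost of an ordinary convention.

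**Conclusion.** The concern holds for AE start dates. This is a stated rule that gives the wrong classification when followed, not a missing detail. A partially dated AE that starts after dosing, in the calendar month or year of first dose, is treated as pre-dose unless first dose fell on the first day of that period. It then leaves the on-treatment AE and AESI summaries unless the worsening clause applies.

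The percentages in step 3 describe partially dated AEs only, and they assume uniform onset within each window and uniform first-dose dates. If AEs cluster just after first dose, the loss within a window would be larger. The documents do not say how many AE dates are partial, so neither the number of events lost nor any effect on the comparison between arms can be computed. Partially dated AEs in later months (or years) move earlier but normally stay on treatment.

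For the win ratio, the expected effect is negligible unless partial endpoint dates are both common and unbalanced between arms.

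**What to change.** Rewrite SAP 2.1.3 as follows:
- Limit the first-of-month and 1 January rule to pre-study history dates.
- AE start: if the known month or year is compatible with the first-dose date, impute the later of the period start and the first-dose date; otherwise use the period start.
- AE end: use the last day of the known period, capped at death or last contact. This is for consistency and changes no specified AE table.
- Deaths and HF hospitalizations: state that the adjudicated date is used, and that any imputed endpoint date may not precede randomization or the last date known event-free.

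Two consequences should be stated openly. The floor will count a truly pre-dose AE in the month or year of first dose as treatment-emergent. The start rule also still pulls some late post-treatment AEs into the window. Both err towards counting more events. Reporting the number of partial AE start dates by arm would show whether either matters.

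The cost is one paragraph in the SAP and routine derivation code. No new data are needed.

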2.2 Analysis sets

Randomized Analysis Set (RAN)

RAN consists of all randomized participants.

Full Analysis Set (FAS)

FAS comprises all participants to whom study treatment has been assigned at randomization. According to the intent to treat principle, participants will be analyzed according to the treatment they have been assigned to during the randomization procedure. Randomization was stratified by country.

However, patients who did not qualify for randomization but were inadvertently randomized into the study and did not receive study medication will be excluded from FAS. Further exclusions from the FAS may only be justified in exceptional circumstances (e.g., serious GCP violations). These potential incidences imply the possibility that the FAS may be smaller than the RAN.

Safety Set (SAF)

SAF includes all participants who received at least one dose of study treatment. Participants will be analyzed according to the study treatment they actually received, where treatment received is defined as the randomized/assigned treatment if the subject took at least one dose of that treatment or the first treatment received if the randomized/assigned treatment was never received.

Per-Protocol Set (PPS)

PPS is a subset of participants of the FAS and will include participants with no major protocol violations and who took at least one dose of the study treatment. Patients with any of the following protocol violations will be excluded from the PPS, but not limited:

- Not fulfilling all the inclusion criteria as described on CLCZ696B3302 Protocol last version;
- Fulfilling any of the exclusion criteria as described on CLCZ696B3302 Protocol last version;

PD definition will be done according to BCRI Work Instruction IT RE 012.

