### **Changes to the protocol**

Changes to specific sections of the protocol are shown in the track changes version as following:

- Sec. 3: Clarifications about remote procedures.
- Sec. 3.2.1: Clarification regarding dose titration for subjects receiving higher dosages of ACEi or ARBs prior to randomization and allocated to the enalapril arm.
- Sec. 4.6: Section added in order to clarify the rationale for implementation of public health emergencies mitigation actions
- Sec. 5.1: Inclusion criteria #4 was edited in order to clarify Chagas' serology accepted tests.
- Sec. 5.2: Exclusion criteria edited in order to add COVID-19 related criteria, add clarification about past use of sacubitril/valsartan and clarify exclusion criterion related to gastrointestinal form of chronic Chagas' disease.
- Sec. 8: note added to table of events.
- Sec. 8.5.1: In the biomarkers section, added that *T. cruzi* serology in addition to parasitemia will be performed.(no additional sample required)
- Sec. 9.1.1: Clarification added to discontinuation of study treatment section.

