## **Summary of previous amendments**

### **Amendment 2 (11-Aug-2020)**

#### **Amendment rationale**

This amendment was implemented to include additional assessments in a subset of participants: biomarkers (approximately 550 patients), Holter monitoring (400 patients), and magnetic resonance imaging (MRI) (100 patients), with the purpose to gain deeper insight into the clinical and molecular mechanisms of CCC and the impact of the study treatments.

The study started on 10-Dec-2019, approximately 12 participants have been recruited to date. The changes proposed by this amendment will not influence the study population. The knowledge obtained from the study results will be enhanced by including the outcomes of the additional assessments.

Information related to re-screening was also included.

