15. History of malignancy of any organ system (other than localized basal or squamous cell carcinoma of the skin or localized prostate cancer), treated or untreated, within the past 5 years, regardless of whether there is evidence of local recurrence or metastases.
16. Current confirmed COVID19 infection
17. Past COVID19 infection with persistent symptom burden suspected due to COVID19 (persistent symptoms may include, but are not limited to, continued cough, breathing difficulty, muscle/joint aches, and gastrointestinal symptoms from the time of COVID19 infection onward)

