This Statistical Analysis Plan (SAP) is based on the protocol for the trial CLCZ696B3302 “A multicenter, prospective, randomized, open-label, blinded-endpoint, Phase 4 study to evaluate the efficacy and safety of sacubitril/valsartan compared with enalapril on morbidity, mortality, and NT-proBNP change in patients with chronic Chagas’ cardiomyopathy”, version 03 (Protocol - 10 November 2021) and describes the statistical methods to be performed in the clinical study report and for the main trial publication.

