2.12 Justification for strategy used in Estimand framework

2.12.1 Primary Estimand

Table 5. Justification for strategy used in Estimand framework

Intercurrent Event	Strategy	Clinical Justification
Treatment discontinuation	Treatment policy	Treatment discontinuation is included in the treatment conditions of interest.
Non-CV death	While Alive	Only data before non-CV death is considered. Death naturally ends the observation period, only the observed part before the non-CV death should be taken into consideration.
Concomitant use of SGLT2 Inhibitor	Treatment policy	Concomitant use of SGLT2 inhibitor is included in the treatment conditions of interest. Use of this concomitant medication will be observed in both arms and is a usual clinical practice.
Covid-19	Treatment policy	Covid-19 is included in the target population of interest.
Treatment crossover (Switch after observing endpoint)	Treatment policy	Treatment crossover is included in the treatment condition of interest (since the switch doesn't have the confounding effect on the observed endpoint)
Treatment crossover (Switch before observing endpoint)	Treatment policy	Treatment crossover is included in the treatment condition of interest

before observing endpoint)		
-------------------------------	--	--

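### The per-protocol set judges all participants against the last protocol version, so a participant correctly enrolled before the COVID-19 exclusions were added can be removed as a violator

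*SAP*

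**What the plan says.** SAP 2.2 describes the PPS as the FAS participants who had no major protocol violations and took at least one dose. It then makes exclusion automatic for two kinds of violation: "Patients with any of the following protocol violations will be excluded from the PPS, but not limited". The two bullets are "Not fulfilling all the inclusion criteria as described on CLCZ696B3302 Protocol last version" and "Fulfilling any of the exclusion criteria as described on CLCZ696B3302 Protocol last version". Neither makes an exception for the version under which a participant was enrolled. A closing line refers the definition of protocol deviations to a work instruction of the research organisation, which is not among the documents.

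The SAP introduction names the protocol it is based on as "version 03 (Protocol - 10 November 2021", which is Amendment 3. The protocol's list of changes for that amendment includes "Exclusion criteria edited in order to add COVID-19 related criteria". In protocol 5.2 these are now criterion 16 (current confirmed infection) and criterion 17: "Past COVID19 infection with persistent symptom burden suspected due to COVID19".

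The rationale for Amendment 2 (11-Aug-2020) records: "The study started on 10-Dec-2019, approximately 12 participants have been recruited to date". The Amendment 3 section states that its changes needed ethics committee or health authority approval under local rules before they could be implemented.

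Protocol 12.1 defines the PPS simply as FAS participants without major deviations. It contains no last-version rule.

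**The concern.** A participant cannot violate a criterion that was not yet in force at the site. A rule that tests everyone against the final text therefore puts two kinds of participant in one class: those who should not have been enrolled under the rules of the day, and those who were enrolled correctly but met a criterion written later. Only the first kind belongs outside a per-protocol set.

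The PPS carries several supportive analyses: the repeat of the primary win ratio, the Cox and Kaplan-Meier analyses of CV death and first HF hospitalisation (SAP 2.5.3), and the SGLT2-inhibitor interaction (SAP 2.8). These are meant to show whether the result holds among adherent participants. If membership depends partly on when someone was enrolled relative to an amendment, the set does not quite measure that.

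There is also a practical problem. One programmer could rely on eligibility as recorded at screening, and another could search medical histories for criteria added later. Both would be following the text, and they could arrive at different sets.

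**Working it through.** The check compares passages and dates. The plan gives no figure for PPS exclusions to reproduce.

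**1. Which version governs.** SAP 2.2 points to the last version. The SAP introduction identifies this as version 03 of 10-Nov-2021. The document history lists the PPS definition among the items updated in SAP version 2.1 (29-Apr-2025), so the current definition was settled well after Amendment 3.

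**2. How long enrolment ran without the added criteria.**
- Study start: 10-Dec-2019 (Amendment 2 rationale).
- Amendment 3: 10-Nov-2021.
- 10-Dec-2019 to 10-Dec-2020 is 366 days, and from there to 10-Nov-2021 is 335 days. 366 + 335 = 701 days; 701 / 30.4375 = 23.0 months.
- This is a minimum, because a site kept the earlier criteria until its local approval arrived.

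**3. Which criteria are new.** The Amendment 3 log describes the changes as follows:

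| Criterion | Described in the log as |
|---|---|
| COVID-19 (exclusions 16 and 17) | added |
| Past sacubitril/valsartan use | clarification |
| Gastrointestinal Chagas' disease | clarification |
| Accepted Chagas' serology tests (inclusion) | clarification |

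Only the COVID-19 criteria are clearly new. Exclusion 11a (systemic infection) is not listed as changed, so current COVID-19 may already have been partly covered. Criterion 17 is the least ambiguous addition.

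**4. What follows for one participant.** Take someone randomised before Amendment 3 applied at the site, with persistent symptoms from a past COVID-19 infection. Protocol 5.2 forbids investigators to add exclusions of their own, and neither the Amendment 2 nor the Amendment 3 log lists a change to that sentence. On that text, enrolling this person followed the protocol. SAP 2.2 nevertheless excludes the same person from the PPS as a violator.

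**5. How many.** The documents give neither the number enrolled before Amendment 3 nor the number who met an added criterion. The only recruitment count is about 12 by August 2020. The range below is an illustration on assumed inputs: 12 to 450 of the planned 900 enrolled earlier, and 0.5% to 5% of these meeting an added criterion.
- Low end: 12 × 0.005 = 0.06, effectively none.
- Middle case: 300 × 0.02 = 6, which is 6 / 900 = 0.67%.
- High end: 450 × 0.05 = 22.5, which is 22.5 / 900 = 2.5%.

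**The case against.** The strongest reply is that the SAP speaks of protocol violations and leaves the definition of deviations to a work instruction. Someone enrolled correctly under an earlier version has violated nothing, so that instruction may already use the version in force. This is possible and cannot be checked. But a general reference does not displace two explicit bullets that name the last version. If the instruction does use the version in force, the SAP contradicts it and still needs correcting.

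The second reply is that the effect is small and confined to a supportive set. This stands. Calendar months are not enrolment volume, and the one recruitment figure available is low. Nor do the documents show that persistent COVID-19 symptoms at entry were recorded before Amendment 3, so few or no such participants may be identifiable. SAP 2.9 also compares participants randomised before 31-Dec-2021 with those randomised later on the primary endpoint, so the enrolment period is examined directly in any case.

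A reader might infer more than the documents support:
- **That early participants are removed as a group.** Only those who meet an added criterion are at risk.
- **That the rule also excuses real breaches of criteria later loosened.** The superseded criteria are not in the documents, and nothing shows that any was loosened.
- **That the rule conflicts with the primary estimand, where** "Covid-19 is included in the target population of interest". That entry treats COVID-19 as an intercurrent event under a treatment policy strategy. Exclusions 16 and 17 concern status at entry, and the estimand is analysed in the FAS.
- **That the open-label design turns this into bias between arms.** The criteria describe participants before randomisation, and no mechanism for different removal by arm is apparent. SAP 2.1 also keeps the trial team blinded until database lock.

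**Conclusion.** The rule is wrong as written, and the severity is minor. Read plainly, SAP 2.2 classes as violators some participants who complied with the protocol in force when they were enrolled. This departs from the SAP's own lead sentence on the PPS and from protocol 12.1, and SAP section 3 does not list it among the changes to protocol-specified analyses.

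The conclusion rests on the wording and the dates: at least 23 months of the study preceded the COVID-19 exclusions. It does not depend on the illustrated count of about 0 to 23, which is assumed and probably generous at its upper end. The consequence is limited to the supportive PPS analyses. The primary win ratio and the secondary efficacy analyses use the FAS and are not affected.

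**What to change.** In both PPS bullets of SAP 2.2, replace the reference to the last protocol version with: *the protocol version approved and in force at the site when the participant was randomised*. State that the same reference governs the classification of deviations under the work instruction. Finalise the PPS list before treatment codes are released.

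The cost is about one sentence in the SAP, plus the date on which each site could begin using Amendment 3. The documents do not say where those dates are held, but protocol 14.1 generally requires approval before an amendment is implemented, so they should be obtainable. The downside is that the PPS will apply slightly different eligibility criteria over time, which the study report can note in a line.
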